### 9.10.2. Trademarks

Trademarks of the GlaxoSmithKline Group of Companies
NONE

Trademarks not owned by the GlaxoSmithKline Group of Companies
SAS
WinNonlin

## 9.11. Appendix 11: List of Data Displays

### 9.11.1. Data Display Numbering

The following numbering will be applied for RAP generated displays:

Section	Tables	Figures
Study Population	1.1 to 1.5	
Safety	2.1 to 2.11	
Pharmacokinetic	3.1 to 3.11	3.1 to 3.11
Section	Listings	
ICH Listings	1 to 50	
Other Listings		

### 9.11.2. Mock Example Shell Referencing

Non IDSL specifications will be referenced as indicated and if required an example mock-up displays provided in the TLF Specification documents.

Section	Figure	Table	Listing
Study Population	POP_Fn	POP_Tn	POP_Ln
Safety	SAFE_Fn	SAFE_Tn	SAFE_Ln
Pharmacokinetic	PK_Fn	PK_Tn	PK_Ln

**NOTES:**

- Non-Standard displays are indicated in the 'IDSL / TST ID / Example Shell' or 'Programming Notes' column as '[Non-Standard] + Reference.'

### 9.11.3. Deliverable [Priority]

Delivery [Priority] 	Description
SAC [X]	Final Statistical Analysis Complete

**NOTES:**

- Indicates priority (i.e. order) in which displays will be generated for the reporting effort.

**9.11.4. Study Population Tables**

Study Population Tables					
No.	Population	IDSL / TST ID / Example Shell	Title	Programming Notes	Deliverable [Priority]
Subject Disposition and Analysis Sets					
1.1	Safety	ES1	Summary of Subject Disposition		SAC [1]
1.2	Screened	ES6	Summary of Reasons for Screening Failures		SAC [1]
1.3	Screened	DV1	Summary of Important Protocol Deviations		SAC [1]
Demographics and Baseline Characteristics					
1.4	Safety	DM1	Summary of Demographic Characteristics		SAC [1]
Medical Conditions and Concomitant Medications					
1.5	Safety	MH1	Summary of Medical Conditions		SAC [1]

## 9.11.5. Safety Tables

Safety : Tables					
No.	Population	IDSL / TST ID / Example Shell	Title	Programming Notes	Deliverable [Priority]
Adverse Events					
2.1	Safety	AE2	Relationship of Adverse Event System Organ Classes, Preferred Terms and Verbatim Text		SAC [1]
2.2	Safety	AE1	Summary of All Adverse Events		SAC [1]
Laboratory Measurements					
2.3	Safety	LB1	Summary of Clinical Chemistry Change from Baseline		SAC [1]
2.4	Safety	LB1	Summary of Haematology Change from Baseline		SAC [1]
2.5	Safety	UR3b	Summary of Urinalysis Dipstick Results		SAC [1]
Electrocardiograms					
2.6	Safety	EG1	Summary of ECG Findings		SAC [1]
2.7	Safety	SAFE_T1	Summary of Frequency of Maximum Post-Dose ECG Parameter Corrected QTc Interval		SAC [1]
2.8	Safety	SAFE_T2	Summary of Frequency of Maximum Change from Baseline for ECG Parameter Corrected QTc Interval		SAC [1]
2.9	Safety	EG2	Summary of Change from Baseline in ECG Values		SAC [1]
Vital Signs					
2.10	Safety	VS1	Summary of Change from Baseline in Vital Signs		SAC [1]

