| 
 1. Subject has a clinically significant abnormality in past medical history or at the Screening physical examination (excluding renal insufficiency and other related stable medical conditions within the renally impaired population of subjects [e.g., hypertension, diabetes, or anemia, which should be stable for at least 3 months before the first dose of study drug]) that in the investigator's opinion may place the subject at risk or interfere with outcome variables of the study. This includes, but is not limited to, history or current cardiac, hepatic, neurologic, gastrointestinal (GI), respiratory, hematologic, or immunologic disease. 2. Subject has any surgical or medical condition (active or chronic) that may interfere with drug absorption, distribution, metabolism, or excretion of the study drug, or any other condition that may place the subject at risk, in the opinion of the investigator. 3. Subject has a functioning renal transplant. 4. Subject with renal impairment has a systolic blood pressure outside the range of 90 to 200 mm Hg, a diastolic blood pressure outside the range of 45 to 110 mm Hg, or a heart rate outside the range of 40 to 120 bpm. 5. Subject with renal impairment has a hemoglobin value <9 g/dL. 6. Female subject has a positive pregnancy test result or is lactating at Screening or upon admission to the clinic. 7. Use of a systemic antibiotic within 30 days of Screening 8. Within 2 months before Screening, either a confirmed history of Clostridium difficile diarrhoea infection or a past positive Clostridium difficile toxin test. 9. Subject has a history of drug and/or alcohol abuse within 6 months before Screening, as determined by the investigator, or subject has a positive drug screen at Screening or upon admission to the clinic. For subjects with renal impairment, a positive drug screen result related to the use of prescription medications is allowed per investigator review and approval, and tetrahydrocannabinol use is allowed per investigator review and approval. 10. History of sensitivity to any of the study drugs, components thereof, or a history of drug or other allergy that, in the opinion of the investigator or GSK medical monitor, contraindicates their participation. 11. History of sensitivity to heparin or heparin-induced thrombocytopenia (if the clinic |

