uses heparin to maintain IV cannula patency).

CONCOMITANT MEDICATIONS

12. Subject has used medications known to affect the elimination of serum creatinine (e.g., trimethoprim or cimetidine) or competitors of renal tubular secretion (e.g., probenecid) within 30 days before dosing.
13. Subjects cannot use any over-the-counter, or prescription medication (except for hormonal contraceptives and/or acetaminophen; see Section 6.11 for more details), vitamin supplement, or herbal medication within 7 days (or 5 half-lives, whichever is longer) before dosing and during the study within 7 days before dosing and during the study. Any exceptions (including subjects with renal impairment that will be on medications during the study) will be discussed with the sponsor or medical monitor on a case-by-case basis and the reasons will be documented.

DIAGNOSTIC ASSESSMENTS AND OTHER CRITERIA

14. Subjects with normal renal function have a presence of hepatitis B surface antigen or positive hepatitis C antibody test result at Screening or within 3 months prior to first dose of study treatment. A subject with renal impairment with stable hepatitis C who has normal liver function test results is allowed with investigator approval.
15. A positive test for human immunodeficiency virus antibody.
16. Subject has clinically significant abnormal findings in serum chemistry, hematology, or urinalysis results obtained at Screening or Day -1 (and Day 7 for Group F only), other than those associated with underlying renal conditions or other stable medical conditions consistent with the disease process.
17. Subject with normal renal function has a baseline corrected QT interval using the Fridericia formula (QTcF) of >450 milliseconds (msec) and subject with renal impairment has a baseline QTcF of >480 msec.

OTHER EXCLUSION CRITERIA

18. Donation of blood in excess of 500 mL within 12 weeks prior to dosing or participation in the study would result in donation of blood or blood products in excess of 500 mL within a 56 day period.
19. Previous exposure to gepotidacin within 12 months prior to the first dosing day.
20. The subject has participated in a clinical trial and has received an investigational product within the following time period prior to the first dosing day in the current study: 30 days, 5 half-lives, or twice the duration of the biological effect of the investigational product (whichever is longer).

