## 9.6. Appendix 6: Values of Potential Clinical Importance

### 9.6.1. ECG

ECG Parameter	Units	Potential Clinically Important Range	
		Lower	Upper
Absolute			
Absolute QTc Interval	msec	> 450	
		> 450	≤ 479
		≥ 480	≤ 499
		≥ 500	
Absolute PR Interval	msec	< 110	> 220
Absolute QRS Interval	msec	< 75	> 110
Change from Baseline			
Increase from Baseline QTc	msec	> 60	
	msec	> 30	≤ 59
	msec	≥ 60	

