### 9.6.2. Vital Signs

Vital Sign Parameter (Absolute)	Units	Potential Clinically Important Range	
		Lower	Upper
Systolic Blood Pressure	mmHg	< 85	> 160
Diastolic Blood Pressure	mmHg	< 45	> 100
Heart Rate	bpm	< 40	> 110

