27	Safety	UR2a	Listing of Urinalysis Toxicities of Grade 3 or Higher		SAC [1]
28	Safety	UR2a	Listing of All Urinalysis Data for Subjects with Toxicities of Grade 3 or Higher		SAC [1]
ECGs					
29	Safety	EG5	Listing of Abnormal ECG Findings		SAC [1]
30	Safety	EG5	Listing of All ECG Findings for Subjects with an Abnormal Finding		SAC [1]

ICH : Listings					
No.	Population	IDSL / TST ID / Example Shell	Title	Programming Notes	Deliverable [Priority]
31	Safety	EG3	Listing of ECG Values of Potential Clinical Importance		SAC [1]
32	Safety	EG3	Listing of All ECG Values for Subjects with Any Value of Potential Clinical Importance		SAC [1]
Vital Signs					
33	Safety	VS4	Listing of Vital Signs of Potential Clinical Importance		SAC [1]
34	Safety	VS4	Listing of All Vital Signs for Subjects with Potential Clinical Importance Values		SAC [1]
Liver Events					
35	Safety	LIVER5	Listing of Liver Monitoring/Stopping Event Reporting	Conditional display	SAC [1]
36	Safety	MH3	Listing of Medical Conditions for Subjects with Liver Stopping Events	Conditional display	SAC [1]
37	Safety	SAFE_L9	Listing of Alcohol Intake at Onset of Liver Event	Conditional display	SAC [1]
38	Safety	PKCL1X	Listing of Plasma Concentration Data for Subjects with Liver Stopping Events	Conditional display	SAC [1]
39	Safety	LIVER7	Listing of Liver Biopsy Details	Conditional display	SAC [1]
40	Safety	LIVER8	Listing of Liver Imaging Details	Conditional display	SAC [1]
Pharmacokinetic					
41	PK	PKCL1X	Plasma Gepotidacin Concentrations by Renal Function	Please list all the concentration data including unscheduled. Repeat for part 2 if needed.	SAC [1]

ICH : Listings					
No.	Population	IDSL / TST ID / Example Shell	Title	Programming Notes	Deliverable [Priority]
42	PK	PKUL1P	Urine Gepotidacin Concentrations by Renal Function	Please list all the concentration data including unscheduled. Repeat for part 2 if needed.	SAC [1]
43	PK	PKCL1X	Saliva Gepotidacin Concentrations by Renal Function	Please list all the concentration data including unscheduled. Repeat for part 2 if needed.	SAC [1]
44	PK	PKCL1X	Dialysate Gepotidacin Concentrations	Please list all the concentration data including unscheduled. Repeat for part 2 if needed.	SAC [1]
45	PK	PKCL1X	Dialyzer Plasma Gepotidacin Concentrations	Please list all the concentration data including unscheduled. Repeat for part 2 if needed.	SAC [1]

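### SAP Table 2.7 counts maximum post-dose QTc above 450 msec in every group, but impaired subjects may enter at up to 480, so the group contrast mixes entry values with post-dose prolongation

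*SAP*

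**What the plan says.** **Entry limits (Protocol 5.2).** Criterion 17 excludes on two different ceilings. The lower one applies to the control groups: "Subject with normal renal function has a baseline corrected QT interval using the Fridericia formula (QTcF) of >450 milliseconds (msec"). The other, 30 msec higher, applies to the remaining groups: "subject with renal impairment has a baseline QTcF of >480 msec". Criterion 4 sets wide vital-sign ranges for impaired subjects only, beginning "Subject with renal impairment has a systolic blood pressure outside the range of 90 to 200 mm Hg". The same criterion allows these subjects a diastolic value from 45 to 110 mm Hg and a pulse from 40 to 120 bpm. Normal subjects have no numeric vital-sign range; Protocol 5.1 leaves it to the investigator.

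**Flag limits (SAP 9.6).** The row "Absolute QTc Interval" has bands >450, >450 to 479, 480 to 499 and 500 msec or more, with no group-specific limit. A separate block, "Increase from Baseline QTc", has >30 to 59 and 60 or more. The vital-sign table, headed "Vital Sign Parameter (Absolute"), flags systolic <85 or >160, diastolic <45 or >100 and heart rate <40 or >110.

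**Displays (SAP 9.11).** Table 2.7 is "Summary of Frequency of Maximum Post-Dose ECG Parameter Corrected QTc Interval". Its title names no baseline category and its programming notes are empty. Table 2.8 tabulates maximum QTc change, Table 2.9 ECG change and Table 2.10 vital-sign change. Vital-sign flags appear only in listings: Listing 33, "Listing of Vital Signs of Potential Clinical Importance", and Listing 34, which gives all values for the flagged subjects.

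**The concern.** The secondary objective compares safety between normal and impaired subjects, and Protocol 4.6.1 names QT prolongation as a risk of the drug. For vital signs the endpoint is change from baseline. For ECG it is simply the readings, so an absolute QTc table displays that endpoint directly.

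Take an impaired subject who enters at QTcF 470 msec and stays there. The drug has done nothing, yet the subject is counted in the >450-479 band of Table 2.7. A normal subject could not have been enrolled at 470. The groups are matched on sex, age and BMI, not on QTc. With about 8 subjects per impaired group, one such subject moves that group's rate by 1/8 = 12.5 points. A reader of the table alone could take an entry criterion for a renal effect on QT, or dismiss a real new crossing as an entry value.

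**Working it through.** The plan states no figure on this point, so there is none to reproduce.

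**Step 1. Entry limits against flag limits.**

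| Measure | Entry, impaired | Entry, normal | SAP flag | Room beyond the flag at entry, impaired |
|---|---|---|---|---|
| QTcF (msec) | up to 480 | up to 450 | >450 | 480 - 450 = 30 |
| Systolic (mm Hg) | 90-200 | no number | <85, >160 | 200 - 160 = 40 above; none below |
| Diastolic (mm Hg) | 45-110 | no number | <45, >100 | 110 - 100 = 10 above; none below |
| Heart rate (bpm) | 40-120 | no number | <40, >110 | 120 - 110 = 10 above; none below |

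For normal subjects the QTcF room is 450 - 450 = 0. No entry value reaches the 500 msec band: even from 480 a rise of 500 - 480 = 20 msec is needed.

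**Step 2. What the ceilings alone can do to Table 2.7.** These are assumptions, since the documents give no QTc mean or SD. Each subject's true QTcF is Normal(mean, between-subject SD), and each ECG adds Normal(0, 8 msec). One pre-dose ECG serves as both entry value and baseline. There are 9 post-dose ECGs (eight from 1.5 to 48 h, plus follow-up), and the tabulated QTc is QTcF. Both groups get the same distribution and no drug effect; only the ceiling differs. I simulated 1,000,000 subjects per row before truncation.

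| Mean / SD (msec) | Pre-dose >450, ceiling 480 | Max >450, ceiling 450 | Max >450, ceiling 480 | Gap (points) | Max >450 among pre-dose 450 or less (ceiling 450 vs 480) |
|---|---|---|---|---|---|
| 410 / 18 | 2.1% | 4.8% | 6.6% | 1.8 | 4.8% vs 4.8% |
| 420 / 20 | 7.9% | 12.3% | 18.7% | 6.4 | 12.3% vs 12.3% |
| 430 / 20 | 16.8% | 21.5% | 34.0% | 12.5 | 21.5% vs 21.5% |
| 440 / 20 | 29.9% | 32.9% | 52.0% | 19.1 | 32.9% vs 32.8% |

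In a group of 8, the expected number already above 450 runs from 8 x 0.021 = 0.2 to 8 x 0.299 = 2.4. A maximum of 480 or more occurs in 0.0% vs 0.1% (mean 410) to 0.2% vs 5.9% (mean 440); 500 or more occurs in at most 0.1%. With a within-subject SD of 5 msec, the gap in the >450 count is 3.7 - 2.3 = 1.4 points at mean 410 and 43.5 - 20.5 = 23.0 at mean 440. The last column shows that the gap vanishes once the pre-dose category is held fixed.

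**Step 3. Whether the change tables cover new crossings.** The lowest change band is >30 msec. Protocol 4.6.1 reports an effect of 12 to 22 msec at 1000 and 1800 mg; this study gives 750 mg. I added an effect to the 1.5 h and 2 h ECGs and took subjects at or below 450 pre-dose whose maximum exceeded 450. At 12 msec, 19-21% of these also rose by more than 30 msec; at 22 msec, 49-51% did. With a within-subject SD of 5 the shares are about 2% and 28-29%. Table 2.8 would thus miss about four in five new crossings or more at the low end, and about half or more at the high end.

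**The case against.** **Much of the plan is already baseline-referenced.** SAP 9.6.1 has QTc change limits, and Tables 2.8 and 2.9 report change. A reader might infer that all the flags rest on absolute values; for QTc the documents do not support that. This stands, but Step 3 shows why change bands do not replace a shift display.

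**New crossings can be traced.** Listing 32 gives all ECG values for any flagged subject, pre-dose included, and the groups are small. A reader might conclude that a new crossing cannot be told from an entry value. That is not so: it can be read from the listing, just not from any listed table.

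**Vital signs.** It is tempting to extend the point to a distorted normal-versus-impaired contrast in blood pressure and heart rate. The documents do not support it. The overlap is at the upper limits only, no by-group table of these flags is listed, the planned summary is change from baseline, and normal subjects have no numeric range to set against the impaired one.

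**A larger size.** If impaired subjects are also assumed to have higher means (420/430/440 against 410), maximum QTc >450 occurs in 5% of normal and 19%/34%/52% of impaired subjects with no drug effect. With a 450 ceiling for both, the impaired figures are still 12%/22%/33%. The ceilings therefore explain only 6.4/13.9 = 46%, 12.5/29.2 = 43% and 19.1/47.2 = 40% of that gap. The rest is the assumed population difference, so those figures should not be charged to the entry criteria.

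**Unseen shells.** Table 2.7 uses the non-standard shell SAFE_T1, kept in a separate specification, which may already carry a baseline category. Numbering in 9.11.1 also runs to Table 2.11, while the list stops at 2.10. This stands as an uncertainty.

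**Conclusion.** The point holds for Table 2.7. In the >450-479 band, and marginally at 480, the by-group contrast mixes entry values with post-dose prolongation, because the entry ceilings differ by 30 msec and the bands do not. No entry value can itself fall in the 500 msec band. The fact of the mixing follows from the documents. Its size does not: about 2 to 19 points under the assumptions of Step 2, and a mean near 410 makes it small. Safety is descriptive, with no testing, and the primary PK analysis is untouched. This is a worthwhile, inexpensive correction to one table, plus a marking in four listings. Neither the entry limits nor any rule for managing subjects is in question.

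**What to change.** **Table 2.7.** Define it in the SAP as a shift table: pre-dose QTcF category (450 or less, >450-479, 480-499, 500 or more) by maximum post-dose category, for each group and each period, with every subject kept in the table. SAP 9.3.2.1 already makes the Day 1 pre-dose ECG the baseline and applies it per period. If SAFE_T1 already has this layout, one SAP sentence saying so closes the point.

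**Listings 31-34.** Mark ECG and vital-sign values that were already beyond the limit pre-dose, and leave every post-dose flag in place. Counting only new crossings would be a mistake: SAP 9.6.2 has a single upper systolic limit, so a subject at 165 mm Hg pre-dose who rose to 210 would drop out of the flags.

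**Cost.** SAP wording, one table shell and one listing column. Pre-dose ECGs and vital signs are already scheduled in every period, so no new data are needed. With about 8 subjects per impaired group the shift cells will be sparse, which is acceptable for a descriptive display.

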9.11.6. Pharmacokinetic Tables

Pharmacokinetic : Tables					
No.	Population	IDSL / TST ID / Example Shell	Title	Programming Notes	Deliverable [Priority]
PK Concentration Data					
3.1	PK	PK01	Summary of Gepotidacin Plasma Pharmacokinetic Concentration-Time Data (units) by Group	Blood samples for PK analysis will be collected at 1 predose time point and 0.25, 0.5, 1.0, 1.5, 2.0, 2.5, 3.0, 4.0, 6.0, 8.0, 12.0, 24 ,36 and 48 hours after dosing. If mean is below the level of quantification, report the mean value as NQ.	SAC [1]
3.2	PK	PK01	Summary of Gepotidacin Urine Concentrations (units)	Urine collection intervals for subjects with normal renal function (Group A and Group D) include 0 (pre-dose), 0 to 2 hours, 2 to 4 hours, 4 to 6 hours, 6 to 8 hours, 8 to 12 hours, 12 to 24 hours, 24 to 36 hours, and 36 to 48 hours. Urine collection intervals for subjects with renal impairment (Group B, Group C, and Group E) include 0 hour (pre-dose), 0 to 6 hours, 6 to 12 hours, 12 to 24 hours, 24 to 36, and 36 to 48 hours. If mean is below the level of quantification, report the mean value as NQ.	SAC[1]

Pharmacokinetic : Tables					
No.	Population	IDSL / TST ID / Example Shell	Title	Programming Notes	Deliverable [Priority]
3.3	PK	PK01	Summary of Gepotidacin Saliva Concentrations (units) by Renal Function	Blood samples for PK analysis will be collected at 1 predose time point and 0.25, 0.5, 1.0, 1.5, 2.0, 2.5, 3.0, 4.0, 6.0, 8.0, 12.0, 24 ,36 and 48 hours after dosing.If mean is below the level of quantification, report the mean value as NQ. Part 1 subjects only.	SAC [1]
3.4	PK	PK01	Summary of Gepotidacin Dialysate Concentrations (units)	Blood samples for PK analysis will be collected at 1 predose time point and 0.25, 0.5, 1.0, 1.5, 2.0, 2.5, 3.0, 4.0, 6.0, 8.0, 12.0, 24 ,36 and 48 hours after dosing. If mean is below the level of quantification, report the mean value as NQ. Part 2 subjects only. Part 2 subjects in Group F only	SAC[1]
3.5	PK	PK01	Summary of Gepotidacin Dialyzer Plasma Concentration (units)	Blood samples for PK analysis will be collected at 1 predose time point and 0.25, 0.5, 1.0, 1.5, 2.0, 2.5, 3.0, 4.0, 6.0, 8.0, 12.0, 24 ,36 and 48 hours after dosing. If mean is below the level of quantification, report the mean value as NQ. Part 2 subjects in Group F only	SAC[1]

Pharmacokinetic : Tables					
No.	Population	IDSL / TST ID / Example Shell	Title	Programming Notes	Deliverable [Priority]
PK Parameters Tables					
3.6	PK Parameters	PKPT4	Summary of Gepotidacin Plasma Parameters by Group	Additional parameters include untransformed and log-transformed for AUC(0-t) (units), AUC(0-∞) (units), Cmax (units);only untransformed – Tmax (units), CL (units), t½ (units), Vss (units), Vz (units), and lambda-z (units). Repeat for part 2 if needed.	SAC [1]
3.7	PK Parameters	PKPT1	Summary of Gepotidacin Urine Pharmacokinetic Parameters by Renal Function	Normal Subjects: Ae(0-2), Ae(2-4), Ae(4-6), Ae(6-8), Ae(8-12), Ae(12-24), Ae(24-36), Ae(36-48), Ae total, fe%, Clr, AUC(0-12), AUC(0-24), AUC(0-48) Renal Impaired: Ae(0-6), Ae(6-12), Ae(12-24), Ae(24-36), Ae(36-48), Ae total, fe%, CLr, AUC(0-12), AUC(0-24), AUC(0-48). Repeat for Part 2.	SAC [1]
3.8	PK Parameters	PKPT4	Summary of Gepotidacin Saliva Pharmacokinetic Parameters by Renal Function	AUC(0-t), AUC(0-∞), Cmax; only untransformed – Tmax, CL, t½, Vz, Vss, RAUC(0-t), RAUC(0-∞) and lambda-z. Part 1 subjects only.	SAC [1]
3.9	PK Parameters	PKPT4	Summary of GSK2140944 Dialysate and Dialyzer Parameters by Group	Arem(0-1), Arem(1-2), Arem(2-3), Arem(3-4), Arem(0-4), AUC(t0-t1), CLD, Frem%(0-4). Part 2 Group F only if needed.	SAC [1]

Pharmacokinetic : Tables					
No.	Population	IDSL / TST ID / Example Shell	Title	Programming Notes	Deliverable [Priority]
PK Analysis Tables					
3.10	PK Parameters	PKPT3	ANOVA of Gepotidacin Plasma Pharmacokinetic Parameters by Renal Function	AUC(0-t), AUC(0-∞), Cmax only log-transformed vs eGFR. Repeat for CrCL. Repeat for Part 2.	SAC [1]
3.11	PK Parameters	PK_T1	Linear Regression of Gepotidacin Plasma Pharmacokinetic Parameters by Renal Function	AUC(0-t), AUC(0-∞), Cmax only log-transformed. Repeat for Part 2.	SAC [1]

## 9.11.7. Pharmacokinetic Figures

Pharmacokinetic : Figures					
No.	Population	IDSL / TST ID / Example Shell	Title	Programming Notes	Deliverable [Priority]
Concentration Plots					
3.1	PK	PKCF4	Mean Gepotidacin Plasma Concentrations by Renal Function (Linear and Semi-Log)	Dashed line represents the LLQ. Present all treatment groups in the same plots.	SAC [1]
3.2	PK	PKCF4	Mean Gepotidacin Urine Concentrations by Renal Function (Linear and Semi-Log)	Dashed line represents the LLQ. Present all treatment groups in the same plots. Plot concentration at the collection midpoint.	SAC [1]
3.3	PK	PKCF4	Mean Gepotidacin Saliva Concentrations by Renal Function (Linear and Semi-Log)	Dashed line represents the LLQ. Present all treatment groups in the same plots.	SAC [1]
3.4	PK	PKCF1P	Individual Gepotidacin Plasma Concentrations by Renal Function (Linear and Semi-Log)	Dashed line represents the LLQ. Present all treatment groups in the same plots.	SAC [1]
3.5	PK	PKCF1P	Individual Gepotidacin Urine Concentrations by Renal Function (Linear and Semi-Log)	Dashed line represents the LLQ. Present all treatment groups in the same plots. Plot concentration at the collection midpoint.	SAC [1]
3.6	PK	PKCF1P	Individual Gepotidacin Saliva Concentrations by Renal Function (Linear and Semi-Log)	Dashed line represents the LLQ. Present all treatment groups in the same plots.	SAC [1]

Pharmacokinetic : Figures					
No.	Population	IDSL / TST ID / Example Shell	Title	Programming Notes	Deliverable [Priority]
Parameter Plots					
3.6	PK Parameters	PK_F1	Scatter Plot to Explore the Relationship between Gepotidacin Plasma Pharmacokinetic Parameters by Renal Function	Present all treatment groups in the same plots. Repeat for CrCL. Repeat for parameter AUC(0-t) and CL	SAC [1]
3.7	PK Parameters	PK_F2	Scatter Plot to Explore the Relationship between Gepotidacin Urine Pharmacokinetic Parameters by Renal Function	Present all treatment groups in the same plots. Repeat for CrCL.	SAC [1]
3.8	PK Parameters	PK_F3	Scatter Plot to Explore the Relationship between Gepotidacin Saliva Pharmacokinetic Parameters by Renal Function	Present all treatment groups in the same plots. Repeat for CrCL. Repeat for parameter AUC(0-t) and CL	SAC [1]
Exploratory Objectives					
3.9	PK	PK_F4	Scatter Plot of Gepotidacin Saliva and Plasma Concentrations by Renal Function	Present all treatment groups in the same plots.	SAC [1]
3.10	PK Parameters	PK_F5	Scatter Plot of Gepotidacin Saliva and Plasma Pharmacokinetic Parameters by Renal function	Present all treatment groups in the same plots. Repeat for parameter AUC(0-t), AUC(0-inf) and CL	SAC [1]

